5.3.2 Drug Concentration Measurements

5.3.2.1 Collection of Samples for Analysis

Blood Samples for Elagolix and Norethindrone Assay

Blood samples for assay of Elagolix and norethindrone, also known as PK samples, will be collected by venipuncture into 3 mL evacuated K_2 -ethylenediaminetetraacetic acid (K_2 EDTA)-containing collection tubes at the time points indicated in Appendix C. Sufficient blood will be collected to provide approximately 1 mL plasma from each sample.

Refer to the study specific laboratory manual for detailed instructions on sample collection, processing and shipment.

The date and time of collection will be recorded on the Central Laboratory Requisition Form. The Day 1 visit sample should be collected approximately 1 hour after the first dose of study drug is administered; samples collected on other visit days will be collected at any time during the visit.

5.3.2.2 Measurement Methods

[figure not shown]
Plasma concentrations of elagolix and norethindrone and serum concentrations of estradiol and progesterone will be determined using validated methods by the Drug Analysis Department at AbbVie. Plasma or serum concentrations of other possible metabolites may be determined with validated or non-validated methods.

5.3.3 Efficacy Variables

5.3.3.1 Primary Efficacy Variable

The primary endpoint will be the percentage of subjects meeting a composite endpoint consisting of these two bleeding assessments:

• MBL volume of < 80 mL during the Final Month (the last 28 days of treatment), AND

• 50% or greater reduction in MBL volume from baseline to the Final Month (the last 28 days of treatment)

A subject who prematurely discontinues the study drug due to adverse events, "lack of efficacy" or "requires surgery or invasive intervention for treatment of uterine fibroids" will be considered as a non-responder regardless whether she meets the two aforementioned responder criteria or not.

5.3.3.2 Secondary Efficacy Variable

The following will be considered secondary variables:

- MBL volume assessed using AH methodology and UBQ
- Suppression of bleeding
- Hemoglobin concentration
- Fibroid and uterine volume

5.3.4 PRO and Quality of Life Variables

- UFS-QoL Questionnaire
- Physician Surgery Questionnaire
- EuroQol (EQ-5D-5L) Questionnaire
- Health Care Resource Utilization (HCRU)
- Patient Global Impression of Change (PGIC) Questionnaires
- Work Productivity and Activity Impairment (WPAI) Questionnaire
- Reason for Study Participation Questionnaire

5.3.5 Safety Variables

- Change from baseline to Month 6 in bone mineral density measured by DXA
- Number and percentage of subjects reporting treatment-emergent adverse events (TEAEs)

- Number and percentage of subjects reporting adverse events of special interest (AESI) (e.g., hypoestrogenic adverse events)
- Time to the first post-treatment menses
- Change from baseline in clinical laboratory parameters
- Change from baseline in vital signs
- Endometrial biopsy and pelvic ultrasound findings
- Columbia Suicide Severity Rating Scale (C-SSRS)

5.3.6 Pharmacodynamic Variables

Concentrations of E2, P, LH and FSH will be obtained throughout the Screening and Treatment Periods. Additional pharmacodynamic parameters may be calculated if useful in the interpretation of the data.

5.3.7 Pharmacokinetic Variables

Exposures of elagolix and norethindrone, may be determined using a population PK approach. Additional parameters may be calculated if useful in the interpretation of the data.

5.3.8 Pharmacogenetic Variables

DNA and RNA samples may be sequenced and data analyzed for RNA expression and genetic factors contributing to the subject's response to elagolix, or other study treatment, in terms of pharmacokinetics, efficacy, tolerability and safety. Such genetic factors may include genes for drug metabolizing enzymes, drug transport proteins, genes within the target pathway, or other genes believed to be related to drug response. Some genes currently insufficiently characterized or unknown may be understood to be important at the time of analysis. The samples may be analyzed as part of a multi-study assessment of genetic factors involved in the response to elagolix or drugs of this class. The samples may also be used for the development of diagnostic tests related to elagolix (or drugs of this class). The results of pharmacogenetic analyses may not be reported with the study summary.

5.3.9 Independent Data Monitoring Committee

An Independent Data Monitoring Committee (IDMC) will be employed for this Phase 3 study and will have the usual responsibilities for safeguarding the interests of study participants and monitoring the overall study conduct. The IDMC will provide recommendations about continuing, modifying, or stopping the trial for safety reasons. The IDMC membership and responsibilities will be documented in its charter. After each IDMC meeting, the IDMC will communicate its recommendations to the sponsor, as described in the IDMC charter.

5.4 Removal of Subjects from Therapy or Assessment

Each subject has the right to withdraw from the study at any time. In addition, the Investigator may discontinue a subject from the study at any time if the Investigator considers it necessary for any reason, including the occurrence of an adverse event or noncompliance with the protocol. Subjects who withdraw from the study will not be replaced unless it is mutually agreed upon, in writing, by the Investigator and AbbVie. Each subject will be withdrawn from the study if any of the following occur:

- The subject decides to withdraw consent for any reason.
- The investigator believes it is in the best interest of the subject.
- Clinically significant deterioration of the subject's medical status as determined by the investigator.
- The subject requires surgical intervention for treatment of uterine fibroids and menstrual bleeding or other procedures including hysterectomy, myomectomy, uterine artery embolization, high intensity focused ultrasound (HIFU), endometrial ablation, dilation and curettage (D&C), etc. during the Treatment Period. In the post treatment period these procedures do not warrant withdrawal if performed during the Post-Treatment Period unless a hysterectomy with bilateral salpingo-oophorectomy (BSO) is performed and the Subject does not plan to use Hormone Replacement Therapy within 1 month of the surgery date.
- The subject becomes pregnant.

- The subject has (SGPT/ALAT) or SGOT/ASAT elevation > 5 times the upper limit of normal confirmed upon repeat during the Treatment Period.
- The subject's legally acceptable representative decides to withdraw consent for any reason.
- Heavy menstrual bleeding during the Treatment Period that requires a blood transfusion at any time after having taken 28 days of study drug. If a subject has a blood transfusion during the Post-Treatment Period, the AbbVie TA MD should be contacted to determine if the subject can remain in the study.
- Any other medical reason that AbbVie or the study investigator deems appropriate.

5.4.1 Discontinuation of Individual Subjects

In the event that a subject withdraws or is prematurely discontinued from study drug treatment, the subject should complete the Treatment Period Premature Discontinuation Visit as soon as possible (preferably within 2 - 7 days of last dose of study drug, if possible) and undergo study procedures as outlined in Appendix C. Subjects who prematurely discontinue during the Treatment Period are expected to enter the 12-Month Post-Treatment Follow-Up Period.

In the event that a subject withdraws or is prematurely discontinued during the Post-Treatment Follow-Up period, the subject should complete the Post-Treatment Premature Discontinuation Visit as soon as possible and undergo study procedures as outlined in Appendix C. These procedures should not interfere with the initiation of any new treatments or therapeutic modalities the Investigator determines are necessary to treat the subject's condition. The reason(s) for the discontinuation from the study will be recorded in the eCRFs.

All used and unused study drug containers will be returned to the study site.

If a subject becomes pregnant during the Treatment or Post-Treatment Follow-Up Periods, no additional study procedures, except an ultrasound will be conducted. Refer to

Section 6.1.6 for instructions on reporting of a pregnancy to the Sponsor and the required follow-up on the subject/fetus and live births.

Subjects who prematurely discontinue from treatment and enter Post-Treatment Follow-Up and received study drug for < 3 months or the procedure was performed in the past two months are not required to undergo the following procedures during the Post-Treatment Period, unless requested by the AbbVie TA MD or based on clinical judgment:

Post-Treatment Period Month 3:

- TAU/TVU
- MRI

Post-Treatment Period Month 6:

- TAU/TVU
- DXA (unless the premature discontinuation was related to BMD decrease or the occurrence of a fracture)

If a subject is discontinued from the study with an ongoing adverse event or an unresolved laboratory result that is clinically significant (as determined by the Investigator), the Investigator will attempt to provide follow-up until a satisfactory clinical resolution of the laboratory result or adverse event is achieved.

5.4.2 Discontinuation of Entire Study

AbbVie may terminate this study prematurely, either in its entirety or at any study site, for reasonable cause provided that written notice is submitted in advance of the intended termination. The Investigator may also terminate the study at his/her site for reasonable cause, after providing written notice to AbbVie in advance of the intended termination. Advance notice is not required by either party if the study is stopped due to safety concerns. If AbbVie terminates the study for safety reasons, AbbVie will immediately

notify the investigator by telephone and subsequently provide written instructions for study termination.

The following procedures for study discontinuation will be followed:

- If the Sponsor has decided to prematurely discontinue the study, the Sponsor will promptly notify in writing the Investigator as well as regulatory authorities of the decision and give detailed reasons for the discontinuation.
- The Investigator must promptly notify the IRB/IEC and give detailed reasons for the discontinuation.
- The Investigator must promptly notify the enrolled subjects of the premature discontinuation and administer appropriate treatments such as replacement of the treatment regimen, if applicable, by other appropriate regimens.

5.4.3 Treatment Interruption

AbbVie or the Investigator may request that a subject temporarily discontinue study drug administration, which will be referred to as "treatment interruption." The following are examples for reasons when the AbbVie TA MD must be notified in order to assess whether a subject should undergo temporary treatment interruption:

- Adverse event, that based on clinical judgment, requires temporary suspension of treatment or prevents a subject from taking study drug
- Due to malfunction of barrier contraception or unprotected intercourse

Additionally, there may be times when a subject has had treatment interruption due to having forgotten to take study medication, lost study medication, etc. If the subject has missed 7 or more consecutive days of dosing (with either ABT-620/Placebo or E2/NETA/Placebo), the AbbVie TA MD must be consulted to determine whether the subject may resume study drug administration or continue in the Treatment Period.

These examples are not all-inclusive; if the Investigator has any questions, these should be directed to the AbbVie TA MD.

5.4.4 Delays in Rollover into the Extension Study

Subjects may be required to remain in the Treatment Period following the completion of the Month 6 visit if results to determine eligibility into the Extension Study are not available at the time of the Month 6 visit. Subjects will return to the study site at the same 28-day monthly visit intervals if eligibility for the extension study has not been determined before then. Subjects will continue to take study drug until eligibility has been established. These visits will be documented as and registered as Unscheduled Visits. Sites should register Unscheduled Visits in IRT in order to obtain additional kits of study drug. Procedures/assessments to be performed during the Unscheduled Visit while the subject is waiting for the determination of eligibility into the extension study, are indicated in the Table 6.

Table 6. Schedule of Assessments - Delays in Roll-Over into Extension Study

Schedule of Assessments – Delays in Roll-Over into Extension Study			
Procedure	Perform Monthly		
Symptom-directed Physical Examination	X		
Vital Signs	X		
Clinical/Safety Laboratory Tests: Hematology, Chemistry ^a	X		
Urine Pregnancy Test ^b	X		
Endocrine Panel: FSH, LH	X		
Pharmacodynamic Sample (PD): Serum Estradiol (E2) and Progesterone (P)	Х		
Contraception Counseling and Dispense Contraceptives as necessary	X		
Dispense Sanitary Products and Collection Kits (Keg, Collection Bags etc.)	Х		
Collect and Return Sanitary Products	Х		
Register Visits in IRT	Х		
Study Drug: Dispense (D) and Return (R) ^c	Х		
Study Drug Accountability	Х		
Study Drug Compliance	Х		
Adverse Event Monitoring	X		
Concomitant Medication Monitoring	Х		
Questionnaires UBQ ^d	Х		
C-SSRS – Since Last Visit	Х		
HCRU	Х		

a. Eight (8) hour minimum fast for Clinical Safety Laboratory Tests; Chemistry and Lipid Panels.

A positive urine pregnancy test result must be confirmed with a quantitative serum pregnancy test. For any subject b. who has a positive serum pregnancy test result, a TVU must be conducted as early as possible in the first trimester in order to assess the gestational age and estimated due date. The subject will be discontinued from the study at the point the pregnancy was confirmed.

[figure not shown]
Urine pregnancy test must be negative prior to providing subjects with their next monthly supply of study drug. c.

The Uterine Bleeding Questionnaire (UBQ) is to be completed by Site Staff at every scheduled monthly visit (or d. PCV) only if the subject did not return a sanitary product collection keg at the visit.

Once eligibility for entry into the extension study has been determined:

Subject Entering the Extension Study:

• Subject will return to the study site as soon as possible

- Subject will discontinue taking study drug from the pivotal study just prior to entering the extension study, i.e., subjects are to continue taking study drug until they have returned to the site for their roll-over visit
- Record transition of study subject into the extension study in IRT

Subject NOT Entering the Extension Study:

- Subject will discontinue taking study drug
- Subject will return to the study site as soon as possible
- Record transition of study subject into the Post-Treatment Follow-up Period in IRT
- The next scheduled visit will be the Month 1 Site Visit

5.5 Treatments

5.5.1 Treatments Administered

Subjects will be randomly assigned by IRT to receive one of the following treatment groups for a total of 6 months of treatment:

- placebo (n = 100)
- elagolix 300 mg BID (n = 100)
- elagolix 300 mg BID plus E2/NETA (estradiol 1.0 mg/norethindrone acetate 0.5 mg) QD (n = 200)

The treatment administration is presented in Table 7.

ObbvieElagolix (ABT-620)
M12-815 Protocol Amendment 3

	Investigational Product				
Treatment Group	Dosing Time	Elagolix 300 mg Tablets	Elagolix Placebo Tablets	E2/NETA Capsules	Matching E2/NETA Placebo Capsules
Placebo	AM	0	1	0	1
	PM	0	1	0	0
Elagolix 300 mg BID	AM	1	0	0	1
	PM	1	0	0	0
Elagolix 300 mg BID plus E2/NETA QD	AM	1	0	1	0
	PM	1	0	0	0

Table 7.Treatments Administered

The elagolix study drug, consisting of elagolix or matching placebo, will be supplied in a carton. The E2/NETA study drug, consisting of E2/NETA or matching placebo, will be supplied in a separate carton. The subject will take the first elagolix dose (morning dose) and first E2/NETA dose of study drug at the study site on Day 1 (Randomization). Subjects will be instructed to self-administer their study drug throughout the 6-month Treatment Period.

A 1-month supply of each study drug (plus 1 week extra) will be dispensed during the Treatment Period at the Day 1 (randomization) Visit, and at the Month 1, 2, 3, 4 and 5 visits.

Study drug will be taken orally twice daily for the entire 6-month Treatment Period. A morning dose of 1 tablet (elagolix or placebo) and 1 capsule (E2/NETA or placebo) and an evening dose of 1 tablet (elagolix or placebo) should be taken each day approximately 12 hours apart. Study drug should be taken with approximately 8 oz. (240 mL) of water without regard to food. Study drug should be taken at approximately the same time each morning and evening in order to promote compliance.

If the subject forgets to take the morning dose, she should be instructed to take the morning dose as soon as possible and take the evening dose as scheduled. If the subject

forgets to take the evening dose, she should be instructed to take the evening dose as soon as possible; if the subject misses the evening dose completely (until the next morning), the subject should only take the morning dose.

On days when the subject visits the study site for the scheduled visits, she will take her morning dose at home, prior to the visit. The evening dose will be taken from the newly dispensed supply of study drug. Subjects must return all study drug containers at each monthly visit.

At the Month 6 visit, a -4 or +6 day visit window will be allowed in order to collect sanitary products from the last menstrual bleeding cycle prior to the Month 6 visit if menstrual bleeding starts immediately prior to or coincides with the scheduled visit. If the +6 day window is needed, the subject will be instructed to continue taking study drug from the extra blister card (1 week supply) until she returns for the Month 6 Visit.

Subjects awaiting results to determine eligibility into the extension study will continue to be dispensed study drug until results are available. Refer to Section 5.4.4 for further details on dispensing and registering subjects during this waiting period.

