Subjects awaiting test results to determine eligibility into the extension study may be required to remain in the Treatment Period to receive additional study drug until results become available. Visits associated with this waiting period will be documented as Unscheduled Visits and subjects will continue to undergo study-related assessments and procedures as outlined in Appendix C and Section 5.4.4 Delays in Rollover into the Extension Study.

Visit Windows

Visit windows will be allowed for the monthly visits during the Treatment and Post-Treatment Follow-Up Periods. Each subsequent monthly visit should be scheduled based on the date of the Day 1 (Randomization) visit. At the Month 6 Treatment Period Visit, a -4 or +6 day visit window will be allowed in order to collect sanitary products from the last episode of menstrual bleeding or spotting prior to the Month 6 visit if ObbvieElagolix (ABT-620)
M12-815 Protocol Amendment 3

menstrual bleeding starts immediately prior to or coincides with the scheduled visit. The subject will be instructed to continue taking study drug from the extra blister card until she returns for the Month 6 visit.

Specific assessment-related visit windows are allowed. Please refer to Table 1, Visit and Assessment Windows, for assessment-specific visit windows.

1 able 1. Visit and Assessment windows	Table 1.	Visit and Assessment Windows
--	----------	------------------------------

Study Visit Windows				
Study Visit	Visit Windows			
Day 1 (Days 1 – 10 of the start of menses)	No visit windows*			
Treatment Period: Months 1 – 5	±4 days			
Treatment Period: Month 6	-4 or +6 days			
Post-Treatment Follow-Up Period: Months 1 – 12	±7 days			
Assessment-Specific Windows for Treatment and Post-Treatment Period				
Study Visit/Assessment	Visit Windows			
Treatment Period				
Day 1: Ultrasound	±7 days			
Day 1: MRI (if participating in MRI subset)	±7 days (unless an MRI was required in Screening. If MRI required in Screening, the Day 1 MRI will not be performed)			
Month 3: Ultrasound	±7 days			
Month 6: Ultrasound, MRI (if participating in MRI subset) DXA Scan and endometrial biopsy	-15 or + 4 days			
Post Treatment Follow-Up Period	·			
Month 3: Ultrasound, MRI (if participating in MRI subset)	-15 or +4 days			
Month 6: Ultrasound, DXA Scan	-15 or +4 days			
Month 12: DXA Scan	-15 or +4 days			

* Randomization must occur between Days 1 - 10 of the onset (first day of full menstrual flow) of menses.

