5.5.2.1 Packaging and Labeling

AbbVie will supply blinded study drug in monthly kits (i.e., cartons). Two kits of study drug will be provided at each dispensing visit. One kit consists of Elagolix or matching placebo and the other kit consists of E2/NETA capsules or matching placebo. Each kit contains 5 blister cards, with each blister card containing 7 days of study medication. There are 4 weekly blister cards and 1 extra medication blister card in each kit to supply enough medication for 4 weeks (28 days) of dosing, plus an extra week's supply.

Each individual elagolix or matching placebo blister card contains 14 tablets for a 7-day (weekly) supply study medication. Also, each E2/NETA or matching placebo blister card contains 7 capsules for a 7-day (weekly) supply of study medication.

The kits will be assigned to a subject via IRT and will encode the appropriate study drug to be dispensed at the subject's corresponding study visit.

The kits and blister cards are labeled as per country requirements. All blank spaces on the label will be completed by the site staff prior to dispensing to the subject. Labels must remain affixed to the study drug containers. Adequate supplies of study drug will be provided to each study site automatically via IRT.

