5.5.2.2 Storage and Disposition of Study Drug

Elagolix, E2/NETA and respective matching placebo study medication must be stored at controlled room temperature 15° to 25°C (59° to 77°F). Additionally, E2/NETA and matching placebo study medication must be protected from light.

The investigational products are for investigational use only and are to be used only within the context of this study. The study drug supplied for this study must be maintained under adequate security and stored under the conditions specified on the label until dispensed for subject use or returned to AbbVie. Returned study drug should not be re-dispensed to the subject.

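### The visit windows allow 38 days between Month 5 and Month 6, but the Month 5 kit holds 35 days of drug, and the SAP does not handle the resulting off-drug days consistently

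*Protocol*

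**What the plan says.** **Windows.** Protocol 5.1 schedules every monthly visit from Day 1, and Table 1 gives Months 1 to 5 a window of ±4 days. "At the Month 6 Treatment Period Visit, a -4 or +6 day visit window will be allowed", so that products can be collected when bleeding starts just before the visit or coincides with it.

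**Supply.** Kits are dispensed at Day 1 and Months 1 to 5 (Protocol 5.5.1). "Each kit contains 5 blister cards, with each blister card containing 7 days of study medication" (5.5.2.1), described there as "enough medication for 4 weeks (28 days) of dosing, plus an extra week's supply". If the +6 days are needed, the woman is to "continue taking study drug from the extra blister card (1 week supply) until she returns for the Month 6 Visit" (5.5.1). No other source is named for that case.

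**Carry-over.** All containers come back at each monthly visit (5.5.1). "Returned study drug should not be re-dispensed to the subject" (5.5.2.2, repeated in 5.5.7).

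**Re-supply.** Protocol 5.3.1.1 describes unscheduled re-supply through IRT for lost or damaged drug. Protocol 5.1 mentions the same situation, but only as an example. Kits for delayed rollover are dispensed at or after the Month 6 visit (5.3.1.1, 5.4.4).

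**Endpoint window.** Protocol 8.1.7.1.1 ends the Final Month on the last dose date. SAP 7.2 ends it on the Reference Day, which by default is the last treatment visit date. SAP 7.4.1 removes from the Treatment Period any AH data obtained after the last dose in Study M12-815.

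**The concern.** The plan treats one spare week as enough for a 6-day hold-over. That is true when Month 5 took place on schedule. Because Month 6 is fixed from Day 1, an early Month 5 visit does not bring Month 6 forward, and the days by which Month 5 was early come out of the same spare week. The protocol never states this condition. A woman who follows every rule can therefore be told to keep dosing until she returns when she has nothing left to take.

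The women affected are those held over because they are bleeding near the end of treatment. Their blood loss on those days is what the window exists to capture and what the primary endpoint measures. Whether it is counted then depends on two SAP rules that use different end dates.

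**Working it through.** **Inputs**

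- Kit: 5 cards x 7 days (Protocol 5.5.2.1). A card holds 14 tablets or 7 capsules.
- Nominal days: Month 5 = 140, Month 6 = 168 (SAP Table 1; a month is 28 days).
- Month 5 offset a: -4 to +4 days. Month 6 offset b: -4 to +6 days (Protocol Table 1).
- Visit days: the morning dose comes from the old supply and the evening dose from the new (Protocol 5.5.1).

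**1. The plan's own figure.** 5 x 7 = 35 days, which matches 28 + 7. Tablets: 5 x 14 = 70. Capsules: 5 x 7 = 35.

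**2. Need.** Gap = (168 + b) - (140 + a) = 28 - a + b. There are as many evening doses as days in the gap, and as many morning doses. Tablets needed = 2 x gap; capsules needed = gap.

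- Month 5 on time, Month 6 at +6: 28 + 6 = 34 days. Covered.
- Month 5 one day early, Month 6 at +6: 28 + 1 + 6 = 35 days. Just covered.
- Month 5 at -4, Month 6 at +6: 28 + 4 + 6 = 38 days. Short by 38 - 35 = 3 days, or 76 - 70 = 6 tablets and 38 - 35 = 3 capsules.

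**3. All whole-day combinations (9 x 11 = 99).** A shortfall needs gap > 35:

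| Month 5 offset | Month 6 offset | Gap (days) | Tablets needed / held | Days short |
|---|---|---|---|---|
| -4 | +4 | 36 | 72 / 70 | 1 |
| -4 | +5 | 37 | 74 / 70 | 2 |
| -4 | +6 | 38 | 76 / 70 | 3 |
| -3 | +5 | 36 | 72 / 70 | 1 |
| -3 | +6 | 37 | 74 / 70 | 2 |
| -2 | +6 | 36 | 72 / 70 | 1 |

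That is 6 of 99: 1 day in three, 2 days in two, 3 days in one.

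**4. Where the days fall.** In the worst case the new kit starts on the evening of Day 136 and its 70th tablet is the morning dose of Day 171. The six tablets from the evening of Day 171 to the morning of Day 174 are not covered, nor are the capsules on the mornings of Days 172, 173 and 174. Planned treatment is 6 x 28 = 168 days, so every Month 6 shortfall lies beyond it.

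**5. Earlier visits.** Between consecutive visits in Months 1 to 5 the longest gap is 28 + 4 + 4 = 36 days, 1 day more than the kit.

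**6. Effect on the Final Month in the worst case, with no further dosing in this study**

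- Protocol definition: Days 171 - 27 = 144 to 171. The uncovered capsule days, 172 to 174, lie outside.
- SAP 7.2 default: Days 174 - 27 = 147 to 174. Days 172 to 174 lie inside, but SAP 7.4.1 removes their AH data. SAP 7.6.1.1 sums the evaluable AH data in the window, so those days add nothing to the total.

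If dosing in M12-815 resumes with a kit dispensed at Month 6, the last dose falls later and blood loss on those days can count.

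**The case against.** The strongest answer is that the case is narrow. It needs a Month 5 visit at least 2 days early together with a Month 6 visit at least 4 days late. Missed doses would stretch the supply. A gap of 1 to 3 days is below the 7 consecutive missed days at which Protocol 5.4.3 requires the sponsor to be consulted. All of this stands, and it limits the size of the problem. It does not remove the contradiction, because the windows permit these visits and the hold-over instruction cannot then be followed.

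Four stronger readings are tempting, and the documents do not support them.

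- **Planned treatment is cut short at Month 6.** It is not. The kit lasts past Day 168 in every combination, and the SAP's Month 6 interval (Days 141 to 168) is untouched by this shortfall. Only the 36-day gap between earlier visits falls within the planned 168 days.
- **A third of held-over women run out.** That figure comes from fixing Month 6 at +6 and assuming that Month 5 visits are evenly spread over the window (3 of 9). The documents give no distribution of visit dates.
- **Final Month volume is understated.** This holds only if dosing in M12-815 does not resume, and only under the SAP definition. A woman dispensed more study drug while she awaits an extension decision has a later last dose.
- **Re-supply is closed to these women.** Protocol 5.1 gives lost or damaged drug as an example, and 5.2.4 refers in general terms to unscheduled visits at which drug is dispensed. A site might use that route, but no passage applies it here.

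**Conclusion.** The visit windows and the kit size contradict each other on the protocol's own figures: up to 38 days allowed against 35 supplied, and up to 36 against 35 between earlier visits. At Month 6 the shortfall is 1 to 3 days in 6 of 99 window combinations, which is not an estimate of how many women are affected. The count assumes whole-day offsets, full adherence and no unscheduled re-supply.

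The link to the primary endpoint is real but conditional. Where dosing in M12-815 does not resume, up to 3 days of the SAP Final Month lose their AH data, and the volume for a woman who is bleeding may be too low. Kit shortage is one route to this. The underlying mismatch is that SAP 7.2 can end the window at a visit while SAP 7.4.1 stops the data at the last dose, and the protocol uses a third arrangement. The documents do not allow the effect on the responder rate, or its direction between arms, to be calculated. The point should be corrected, but it does not undermine the trial.

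**What to change.** Two reconciliations are needed.

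1. **Supply and windows.** Bring Protocol 5.1 (Visit Windows and Table 1), 5.5.1, 5.5.2.1, 5.5.2.2 and the re-supply text in 5.3.1.1 into agreement, so that the drug a woman holds and the visit dates she is allowed are compatible, including between Months 1 and 5. How this is done is for the sponsor to decide; no dosing or dispensing rule is proposed here.
2. **Final Month and AH data.** Align the definitions in Protocol 8.1.7.1.1 and SAP 7.2 with the exclusion in SAP 7.4.1, so that AH data collected up to the Month 6 visit are treated the same way for every subject, whether or not dosing in M12-815 continues afterwards.

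The cost is a few sentences in each document. Any supply or scheduling cost depends on how the sponsor resolves the first item.
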